10.3.3. Recording/Reporting and Follow-up of AEs and/or SAEs

AE and SAE Recording/Reporting

The table below summarizes the requirements for recording adverse events on the CRF and for reporting serious adverse events on the CT SAE Report Form to Pfizer Safety. These requirements are delineated for 3 types of events: (1) SAEs; (2) nonserious adverse events (AEs); and (3) exposure to the study intervention under study during pregnancy or breastfeeding, and occupational exposure.

It should be noted that the CT SAE Report Form for reporting of SAE information is not the same as the AE page of the CRF. When the same data are collected, the forms must be completed in a consistent manner. AEs should be recorded using concise medical terminology and the same AE term should be used on both the CRF and the CT SAE Report Form for reporting of SAE information.

Safety Event	Recorded on the CRF	Reported on the CT SAE Report Form to Pfizer Safety Within 24 Hours of Awareness
SAE	All	All
Nonserious AE	All	None
Exposure to the study intervention under study during pregnancy or breastfeeding, and occupational exposure	All AEs/SAEs associated with exposure during pregnancy or breastfeeding Occupational exposure is not recorded.	All (and EDP supplemental form for EDP) Note: exclude all SAEs associated with exposure during pregnancy or breastfeeding. exclude all AEs/SAEs associated with occupational exposure.

- When an AE/SAE occurs, it is the responsibility of the investigator to review all documentation (eg, hospital progress notes, laboratory reports, and diagnostic reports) related to the event.
- The investigator will then record all relevant AE/SAE information in the CRF.
- It is **not** acceptable for the investigator to send photocopies of the participant's medical records to Pfizer Safety in lieu of completion of the CT SAE Report Form/AE/SAE CRF page.
- There may be instances when copies of medical records for certain cases are requested by Pfizer Safety. In this case, all participant identifiers, with the exception of the participant number, will be redacted on the copies of the medical records before submission to Pfizer Safety.
- The investigator will attempt to establish a diagnosis of the event based on signs, symptoms, and/or other clinical information. Whenever possible, the diagnosis (not the individual signs/symptoms) will be documented as the AE/SAE.

Assessment of Intensity

The investigator will make an assessment of intensity for each AE and SAE reported during the study and assign it to 1 of the following NCI CTCAE grading categories:

GRADE	Clinical Description of Severity
1	MILD adverse event
2	MODERATE adverse event
3	SEVERE adverse event
4	LIFE-THREATENING consequences; urgent intervention indicated
5	DEATH RELATED TO adverse event

Note: CRS will be assessed according to the modified grading described by ASTCT as described in [Appendix 9](#).

An event is defined as "serious" when it meets at least 1 of the predefined outcomes as described in the definition of an SAE, NOT when it is rated as severe.

Assessment of Causality

- The investigator is obligated to assess the relationship between study intervention and each occurrence of each AE/SAE.
- A "reasonable possibility" of a relationship conveys that there are facts, evidence, and/or arguments to suggest a causal relationship, rather than a relationship cannot be ruled out.
- The investigator will use clinical judgment to determine the relationship.
- Alternative causes, such as underlying disease(s), concomitant therapy, and other risk factors, as well as the temporal relationship of the event to study intervention administration, will be considered and investigated.
- The investigator will also consult the IB and/or product information, for marketed products, in his/her assessment.
- For each AE/SAE, the investigator **must** document in the medical notes that he/she has reviewed the AE/SAE and has provided an assessment of causality.
- There may be situations in which an SAE has occurred and the investigator has minimal information to include in the initial report to the sponsor. However, **it is very important that the investigator always make an assessment of causality for every event before the initial transmission of the SAE data to the sponsor.**
- The investigator may change his/her opinion of causality in light of follow-up information and send an SAE follow-up report with the updated causality assessment.
- The causality assessment is one of the criteria used when determining regulatory reporting requirements.
- If the investigator does not know whether or not the study intervention caused the event, then the event will be handled as "related to study intervention" for reporting purposes, as defined by the sponsor. In addition, if the investigator determines that an SAE is associated with study procedures, the investigator must record this causal relationship in the source documents and CRF, and report such an assessment in the dedicated section of the CT SAE Report Form and in accordance with the SAE reporting requirements.

Follow-up of AEs and SAEs

- The investigator is obligated to perform or arrange for the conduct of supplemental measurements and/or evaluations as medically indicated or as requested by the sponsor to elucidate the nature and/or causality of the AE or SAE as fully as possible. This may include additional laboratory tests or investigations, histopathological examinations, or consultation with other healthcare providers.
- New or updated information will be recorded in the originally completed CRF.
- The investigator will submit any updated SAE data to the sponsor within 24 hours of receipt of the information.

10.3.4. Reporting of SAEs**SAE Reporting to Pfizer Safety via an Electronic Data Collection Tool**

- The primary mechanism for reporting an SAE to Pfizer Safety will be the electronic data collection tool.
- If the electronic system is unavailable, then the site will use the paper SAE data collection tool (see next section) in order to report the event within 24 hours.
- The site will enter the SAE data into the electronic system as soon as the data become available.
- After the study is completed at a given site, the electronic data collection tool will be taken off-line to prevent the entry of new data or changes to existing data.
- If a site receives a report of a new SAE from a study participant or receives updated data on a previously reported SAE after the electronic data collection tool has been taken off-line, then the site can report this information on a paper SAE form (see next section) or to Pfizer Safety by telephone.

SAE Reporting to Pfizer Safety via CT SAE Report Form

- Facsimile transmission of the CT SAE Report Form is the preferred method to transmit this information to Pfizer Safety.
- In circumstances when the facsimile is not working, notification by telephone is acceptable with a copy of the CT SAE Report Form sent by overnight mail or courier service.

- Initial notification via telephone does not replace the need for the investigator to complete and sign the CT SAE Report Form pages within the designated reporting time frames.

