8.3.5.1. Exposure During Pregnancy

An EDP occurs if:

- A female is found to be pregnant while being exposed or having been exposed to study intervention due to environmental exposure. Below are examples of environmental exposure during pregnancy:
 - A female family member or healthcare provider reports that she is pregnant after having been exposed to the study intervention by accidental injection or contact of study intervention with mucous membranes or open wounds.
 - A male family member or healthcare provider who has been exposed to the study intervention by accidental injection or contact of study intervention with mucous membranes or open wounds then exposes his female partner prior to or around the time of conception.

The investigator must report EDP to Pfizer Safety within 24 hours of the investigator's awareness, irrespective of whether an SAE has occurred. The initial information submitted

should include the anticipated date of delivery (see below for information related to termination of pregnancy).

- If EDP occurs in a participant or a participant's partner, the investigator must report this information to Pfizer Safety on the CT SAE Report Form and an EDP Supplemental Form, regardless of whether an SAE has occurred. Details of the pregnancy will be collected after the start of study intervention and until 4 months after the last dose.
- If EDP occurs in the setting of environmental exposure, the investigator must report information to Pfizer Safety using the CT SAE Report Form and EDP Supplemental Form. Since the exposure information does not pertain to the participant enrolled in the study, the information is not recorded on a CRF; however, a copy of the completed CT SAE Report Form is maintained in the investigator site file.

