Follow-up is conducted to obtain general information on the pregnancy and its outcome for all EDP reports with an unknown outcome. The investigator will follow the pregnancy until completion (or until pregnancy termination) and notify Pfizer Safety of the outcome as a follow-up to the initial EDP Supplemental Form. In the case of a live birth, the structural integrity of the neonate can be assessed at the time of birth. In the event of a termination, the reason(s) for termination should be specified and, if clinically possible, the structural integrity of the terminated fetus should be assessed by gross visual inspection (unless preprocedure test findings are conclusive for a congenital anomaly and the findings are reported).

Abnormal pregnancy outcomes are considered SAEs. If the outcome of the pregnancy meets the criteria for an SAE (ie, ectopic pregnancy, spontaneous abortion, intrauterine fetal demise, neonatal death, or congenital anomaly), the investigator should follow the procedures for reporting SAEs. Additional information about pregnancy outcomes that are reported to Pfizer Safety as SAEs follows:

- Spontaneous abortion including miscarriage and missed abortion;
- Neonatal deaths that occur within 1 month of birth should be reported, without regard to causality, as SAEs. In addition, infant deaths after 1 month should be reported as SAEs when the investigator assesses the infant death as related or possibly related to exposure to the study intervention.

Additional information regarding the EDP may be requested by the sponsor. Further follow-up of birth outcomes will be handled on a case-by-case basis (eg, follow-up on preterm infants to identify developmental delays). In the case of paternal exposure, the investigator will provide the participant with the Pregnant Partner Release of Information Form to deliver to his partner. The investigator must document in the source documents that the participant was given the Pregnant Partner Release of Information Form to provide to his partner.

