8.3.5.3. Occupational Exposure

An occupational exposure occurs when a person receives unplanned direct contact with the study intervention, which may or may not lead to the occurrence of an AE. Such persons may include healthcare providers, family members, and other roles that are involved in the trial participant's care.

The investigator must report occupational exposure to Pfizer Safety within 24 hours of the investigator's awareness regardless of whether there is an associated SAE. The information must be reported using the CT SAE Report Form. Since the information does not pertain to a participant enrolled in the study, the information is not recorded on a CRF; however, a copy of the completed CT SAE Report Form is maintained in the investigator site file.

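### The Appendix 3 reporting table tells sites to leave exposure-associated SAEs off the 24-hour form, in conflict with Sections 8.3.1.1 and 8.3.5 and with its own entries

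*Protocol*

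**What the plan says.** The table in Protocol 10.3.3 (Appendix 3) summarises what goes on the CRF and what goes to the sponsor's safety group on the CT SAE Report Form within 24 hours. Its SAE row says All in both columns. Its nonserious AE row says All for the CRF and None for the form.

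In the exposure row, the form column starts with All, adding the EDP supplemental form where it applies. It then carries a note to "exclude all SAEs associated with exposure during pregnancy or breastfeeding" and, in a second sentence, to "exclude all AEs/SAEs associated with occupational exposure". The CRF column lists "All AEs/SAEs associated with exposure during pregnancy or breastfeeding" and adds "Occupational exposure is not recorded".

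The body of the protocol says the following:
- **8.3.5:** exposure during pregnancy, exposure during breastfeeding and occupational exposure all go to the safety group within 24 hours.
- **8.3.5.1:** pregnancy exposure in a participant or partner is reported "on the CT SAE Report Form and an EDP Supplemental Form, regardless of whether an SAE has occurred". The section also states "Abnormal pregnancy outcomes are considered SAEs" and routes them through SAE reporting.
- **8.3.5.2:** breastfeeding exposure goes on the same form in the same time, with or without an SAE.
- **8.3.5.3:** occupational exposure goes on the same form within 24 hours, "regardless of whether there is an associated SAE".
- **8.3.1.1:** every SAE in a participant during the active collection period goes on the form within 24 hours, with no exception for exposure.

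**The concern.** Site staff are likely to use the summary table when deciding what to send, and Sections 8.3.1.1 and 8.3.2 both point them to Appendix 3. As worded, the note removes the serious outcomes, which are the most informative part of an exposure report.

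This is a first-in-human study. Section 4.2 says that no reproductive or developmental toxicity studies were done and that teratogenicity is considered possible. Congenital anomaly is itself an SAE criterion in 10.3.2. Prompt notice of such an outcome, or of a serious event in an exposed staff member, is what the 24-hour rule exists to secure.

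**Working it through.** No arithmetic applies. The check sets the note against the rest of the protocol for each exposure type.

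| Exposure | Note in 10.3.3, 24-hour form | Section 8.3.5 | CRF column of the table | Result |
|---|---|---|---|---|
| Pregnancy | Associated SAEs excluded | Form required with or without an SAE; abnormal outcomes are SAEs (8.3.5.1) | Associated AEs/SAEs recorded | Conflict; CRF record remains |
| Breastfeeding | Associated SAEs excluded | Form required with or without an SAE (8.3.5.2) | Associated AEs/SAEs recorded | Conflict; CRF record remains |
| Occupational | Associated AEs and SAEs excluded | Form required with or without an SAE (8.3.5.3) | Not recorded | Conflict; no CRF record |

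1. **Within the cell.** It opens with All and then removes a subset. An exposure without an SAE would be sent, while the SAE arising from an exposure would not.
2. **Within the table.** The SAE row says All for the form, without qualification.
3. **Against 8.3.1.1.** That section covers SAEs in participants, so it contradicts the pregnancy and breastfeeding sentence. It does not reach an exposed staff member; for occupational exposure the conflict is with 8.3.5 and 8.3.5.3.
4. **Extent of the CRF fallback.** It is firm for events in participants. Sections 8.3.5.1 and 8.3.5.2 keep environmental exposures of non-participants off the CRF, with a copy of the form held in the site file. Section 8.3.5.3 does the same for occupational exposure.

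**The case against.** The strongest objection is that the word may be an extraction error. The finding depends on *exclude* in one cell of a table read from PDF. The second instance is lower case after a full stop. Whole words look misread elsewhere: *scanning* among the biopsy-site effects in 2.3.1, *Patient 1* where Part 1 seems meant in 9.4.3.1, and *none-mediated* myocarditis in the Appendix 14 cardiac table. A note saying *include* would fit the cell, the SAE row and Section 8.3.5. This is plausible but unproven, because the word appears twice, in two coherent sentences. It calls for a check of the source PDF and does not justify dismissing the point.

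A second objection is that the note may only avoid duplication, since the SAE row already captures SAEs. The table does not say so. The reading also fails for nonserious occupational AEs: the nonserious row sends nothing to the form and occupational exposure is not on the CRF.

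A third objection is that Section 8.3.5 is explicit, and a site following it would report correctly. That stands, and it limits the consequence. It does not remove the conflict from a table that states it summarises the requirements.

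**Conclusion.** On the supplied text the contradiction is real for all three exposure types. A site relying on the table could miss 24-hour reporting of a serious exposure outcome. Occupational exposure is the most vulnerable, because the note there covers AEs as well as SAEs and the CRF holds no record.

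A reader might infer more than the documents support:
- *That no exposure-associated SAE would reach the safety group.* The cell's opening All and the SAE row both point the other way. The table contradicts itself; it is not a clean exclusion.
- *That a missed case is lost entirely.* The table keeps pregnancy and breastfeeding AEs/SAEs on the CRF, and 8.3.5.1 requires the pregnancy outcome to be notified as follow-up to the initial EDP Supplemental Form.
- *That an occupational SAE is captured nowhere.* This holds only if the site also disregards 8.3.5.3.
- *That pregnancies are followed only to 4 months after the last dose.* That is the window for collecting pregnancy details; 8.3.5.1 follows the pregnancy itself to completion or termination.
- *That these SAEs are the study's only human reproductive-safety signals.* Exposures without an SAE are reported too.

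The size cannot be put as a number, since the documents give no expected count or rate of exposure events. Sample size, error rates, endpoints and dose decisions are untouched. The conclusion assumes that the source PDF does read *exclude*; if it does not, the point falls.

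**What to change.** Check the two sentences in the 10.3.3 note against the source PDF. If both read *exclude*, change each to *include*, so that SAEs associated with pregnancy or breastfeeding exposure, and AEs/SAEs associated with occupational exposure, go on the CT SAE Report Form as Section 8.3.5 already requires. Add a cross-reference from the table to Section 8.3.5 and notify sites. The cost is two words, one cross-reference and a site notification. No assessment, dose or analysis changes.

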10.4. Appendix 4: Contraceptive Guidance

10.4.1. Male Participant Reproductive Inclusion Criteria

Male participants are eligible to participate if they agree to the following requirements during the intervention period and for at least 4 months after the last dose of study intervention, which corresponds to the time needed to eliminate reproductive safety risk of the study intervention(s):

- Refrain from donating sperm.

PLUS either:

- Be abstinent from heterosexual intercourse with a female of childbearing potential as their preferred and usual lifestyle (abstinent on a long-term and persistent basis) and agree to remain abstinent.

OR

- Must agree to use a male condom when engaging in any activity that allows for passage of ejaculate to another person.

10.4.2. Female Participant Reproductive Inclusion Criteria

A female participant is eligible to participate if she is not pregnant or breastfeeding, and at least 1 of the following conditions applies:

- Is not a WOCBP (see definitions below in Appendix 4, Section 10.4.3).

OR

- Is a WOCBP and using a contraceptive method that is highly effective (with a failure rate of <1% per year), preferably with low user dependency, as described below during the intervention period and for at least 4 months after the last dose of study intervention, which corresponds to the time needed to eliminate any reproductive safety risk of the study intervention(s). The investigator should evaluate the effectiveness of the contraceptive method in relationship to the first dose of study intervention.

The investigator is responsible for review of medical history, menstrual history, and recent sexual activity to decrease the risk for inclusion of a woman with an early undetected pregnancy.

10.4.3. Woman of Childbearing Potential

A woman is considered fertile following menarche and until becoming postmenopausal unless permanently sterile (see below).

If fertility is unclear (eg, amenorrhea in adolescents or athletes) and a menstrual cycle cannot be confirmed before the first dose of study intervention, additional evaluation should be considered.

Women in the following categories are not considered WOCBP:

1. Premenopausal female with 1 of the following:

- Documented hysterectomy;
- Documented bilateral salpingectomy;
- Documented bilateral oophorectomy.

For individuals with permanent infertility due to an alternate medical cause other than the above, (eg, mullerian agenesis, androgen insensitivity), investigator discretion should be applied to determining study entry.

Note: Documentation for any of the above categories can come from the site personnel's review of the participant's medical records, medical examination, or medical history interview. The method of documentation should be recorded in the participant's medical record for the study.

2. Postmenopausal female.

- A postmenopausal state is defined as no menses for 12 months without an alternative medical cause. In addition, a
 - High FSH level in the postmenopausal range must be used to confirm a postmenopausal state in women under 60 years old and not using hormonal contraception or HRT.
 - Female on HRT and whose menopausal status is in doubt will be required to use one of the nonestrogen hormonal highly effective contraception methods if they wish to continue their HRT during the study. Otherwise, they must discontinue HRT to allow confirmation of postmenopausal status before study enrollment.

10.4.4. Contraception Methods

Contraceptive use by men or women should be consistent with local availability/regulations regarding the use of contraceptive methods for those participating in clinical trials.

Highly Effective Methods That Have Low User Dependency

1. Implantable progestogen-only hormone contraception associated with inhibition of ovulation
2. Intrauterine device (IUD)

3. Intrauterine hormone-releasing system (IUS)
4. Bilateral tubal occlusion
5. Vasectomized partner
 - Vasectomized partner is a highly effective contraceptive method provided that the partner is the sole sexual partner of the WOCBP and the absence of sperm has been confirmed. If not, an additional highly effective method of contraception should be used. The spermatogenesis cycle is approximately 90 days.

Highly Effective Methods That Are User Dependent

1. Combined (estrogen- and progestogen-containing) hormonal contraception associated with inhibition of ovulation.
 - Oral;
 - Intravaginal;
 - Transdermal;
 - Injectable.
2. Progestogen-only hormone contraception associated with inhibition of ovulation.
 - Oral;
 - Injectable.
3. Sexual abstinence.
 - Sexual abstinence is considered a highly effective method only if defined as refraining from heterosexual intercourse during the entire period of risk associated with the study intervention. The reliability of sexual abstinence needs to be evaluated in relation to the duration of the study and the preferred and usual lifestyle of the participant.

One of the following effective barrier methods must be used in addition to the highly effective methods listed above that are user dependent:

- Male or female condom with or without spermicide;
- Cervical cap, diaphragm, or sponge with spermicide;

- A combination of male condom with either cervical cap, diaphragm, or sponge with spermicide (double-barrier methods).

